To allow for intention-to-treat analysis, all randomized patients will be followed up for the primary endpoint, whether or not they complete the scheduled treatment. The patient should be observed for at least 10 years after randomization. However, patients prematurely discontinuing their study participation will have their data deleted upon their request.

WITHDRAWAL, INVESTIGATORS DECISION

Once a subject has been included in the study, the investigator can if he/she thinks it's necessary, exclude patient from study participation out of e.g. safety reasons (e.g. SAE or another inter-current illness violating the conditions of the study). Other reasons, than safety, for discontinuing patients from study could be the following:

- 1 Subject not willing to cooperate
- 2 Subjects lost to follow-up
- 3 Non compliance of patient

Whenever such decision is made full assessment of the patient should be carried out (if possible) according to this protocol. The discontinuation should be documented in the patient's medical record and in patient's eCRF. The documentation shall consist of: date and time of the withdrawal and the reasons for withdrawal. If a subject discontinues his participation in the study, the subject number cannot be reused

INTERVENTION

EXPERIMENTAL STUDY ARM

Open retro-pubic or minimally invasive radical prostatectomy. Concurrent extended pelvic lymph-node dissection is strongly recommended in the protocol but may be omitted if local guidelines at participating sites recommend otherwise.

The extended lymph-node dissection shall be done as described by Heidenreich A et al (52) and includes the obturator fossa, the external and internal iliac nodes, and common iliac nodes up to the ureteric crossing. For handling of surgical biopsy specimen, see Appendix A: Standard Operating Procedure (SOP A) Specimen Handling of pathological Specimen.

The experimental study arm includes immediate postoperative radiation to the prostate bed in selected clinical situations depending on the likelihood of remaining local disease after surgery (see flow chart below). Postoperative radiotherapy includes 18 months of treatment with Bicalutamide 150 mg daily.

In general oncology, adjuvant treatment is a treatment given after the primary treatment to lower the risk of tumor recurrence (www.cancer.gov). This inherently implies no signs of remaining disease. Salvage treatment, on the other hand, is defined as treatment given after the cancer has not responded to other treatments. In prostate cancer, the demarcation between adjuvant and salvage has been drawn a certain time after the primary treatment, for example 6 months. To avoid misunderstanding, we will consistently use the words immediate and deferred RT.

The algorithms for immediate and deferred postoperative radiotherapy are depicted separately for pT2 and pT3 tumors in the Figures 1 and 2 below. It should be noted that positive surgical margins range from focal/clinically insignificant to multifocal and/or extensive. Moreover, the prognostic implications of lymph-node-positive disease vary greatly with the number and percentage of affected lymph nodes, and postoperative PSA levels can range from barely measurable to high. Therefore, there can be no firm guidelines for postoperative radiotherapy. The flow chart therefore suggests what we consider the most likely regimen in each scenario, but the treating clinician should decide whether or not the suggestions are applicable in each case, preferably at multidisciplinary therapy conferences. Deviance from the suggested regimens, however, shall be recorded in the case report forms.

The postoperative radiotherapy protocol is specified in Appendix B.

REFERENCE STUDY ARM (NON-EXPERIMENTAL)

Regardless of type of radiation treatment, patients will be prescribed 3 months neoadjuvant and 3 months adjuvant maximal androgen blockade (LHRH + antiandrogen 150 mg x 1) followed by 18 months antiandrogen (bicalutamide 150 mg. x 1) treatment (or, alternatively, 18 months of LHRH if single treatment with bicalutamide is not compatible with local treatment standards). Prolonged administration of AA or LHRH is accepted for up to 30 months after the last radiation dose is acceptable if required by local guidelines. Prophylactic radiation to the mammary glands should be done to reduce painful gynecomastia during AA treatment. The RT in the non-experimental arm is specified in the Appendix B

RANDOMIZATION

Patients who meet all inclusion criteria and none of exclusion criteria after screening will be included in the study and randomized to one of the two parallel arms in a 1:1 fashion. Patients will be entered into the study in a strict sequence as their ability for enrolment is confirmed. The subjects are either randomized in to the experimental arm: radical prostatectomy or to the reference arm: radiotherapy. The randomization is stratified by site in order to balance the allocation at each center. The actual randomization is web-based and is performed in the eCRF database after checking inclusion and exclusion criteria.

ETHICAL CONSIDERATIONS AND INSURANCE

This study will be conducted according to ICH-GCP, national law and guidelines and the Helsinki declaration. Before patient inclusion starts, this study protocol will be approved by an ethical review board in each country.

There is no specific insurance for participating subjects, who are covered by the regular health-care insurance plan in their respective country.

STUDY MANAGEMENT

MONITORING

A monitor will check the accuracy of the randomization procedure and check that personnel is familiar with the concept of data recording and reporting according to ICH-GCP in medical records and in eCRF. Monitor will visit the site during the study regularly to conduct source data verification, and also perform a study close out visit after the study has ended to close the site and gather essential documents to sponsor.

Data verification will be performed on 10% of patients after the entry of at least 10 patients. The site file will also be reviewed. We plan to perform regular monitoring visits once a year. The frequency of visits may increase if any specific issues arise. The institution is responsible for ensuring that all relevant materials are available for review including the trial master file, case report forms and patient source documents.

ARCHIVING

The investigator will keep all physical records from the study for 10 years after the final clinical study report under safe conditions.

DATA MANAGEMENT

Data management based on ICH-GCP refers to the activities defined to achieve safe routines to efficiently enter patient information into a database, avoiding errors. The database, data entry screens, and program will be designed in accordance with the clinical trial protocol.

CASE REPORT FORMS

If there is truly no difference between standard and new treatments, then 1120 patients are required to be 90% sure that the upper limit of a one-sided 95% confidence interval (or equivalently a 90% two-sided confidence interval) will exclude a difference in favor of the standard treatment of more than 7%.

PUBLICATION POLICIES

The current protocol is registered on www.clinicaltrials.gov prior to commencement of the study in accordance with the guidelines of The International Committee of Medical Journal Editors (ICMJE).

The results from this study will be published irrespective of them being positive or negative. Co-authorship will be granted in accordance with the Uniform Requirements for Manuscript Submitted to Biomedical Journals (URMs; http://www.icmje.org/recommendations/browse/about-the-recommendations/history-of-the-recommendations.html) provided response to manuscript drafts and correspondence in a timely manner. The opportunity to co-author manuscripts will be offered all members of the Trial Management Group (listed above in the Contact Information) and one representative from each participating center contributing with more than 5% of evaluable patients (2 representatives if contributing with more than 30%), and to the statistician who has contributed to collecting/validating and analyzing data, and other persons who have contributed substantially to the implementation and/or evaluation of the trial. Centers contributing with less than 5% of evaluable patients may combine their contribution with another center and share co-authorship alternating. Investigators at participating centers who do not qualify as co-authors will be listed as non-author contributors.

The principal investigator is responsible for carrying out a draft manuscript for discussion among the coauthors. After the results regarding the primary and secondary endpoints of the whole study cohort have been published, investigators are allowed to publish data regarding the primary and secondary endpoints from their own institution if the manuscript has been shown to the Trial Management Group before submission.

The results from different centers will be analyzed together and published as soon as possible. Individual groups/clinicians must not publish data concerning their patients that are directly relevant to questions posed by the study until the Trial Management Group has published its report. The Trial Management Group will form the basis of the Writing Committee and will advise on the nature of all publications. Studies using SPCG-15 data to evaluate endpoints other than those specified in this protocol can be published by the participating institution(s) after approval from the Trial Management Group.

DEFINITION OF CLINICAL EVENTS AND SUGGESTED TREATMENT

In this study, urologists do follow up of operated patients, whereas oncologists do follow up of patients subjected to radiotherapy. Given that modern medical treatment of advanced prostate cancer prolongs survival, the differential follow up is a potential source of bias in the comparison of survival. Therefore, to standardize decision making, all patients with suspected biochemical progression or CRPC shall be discussed in multidisciplinary therapy conferences involving urologists as well as oncologists.

BIOCHEMICAL PROGRESSION

Radiotherapy arm: Biochemical progression in the radiotherapy arm will use the *Phoenix definition of progression*.(64)(No biological evidence of disease is defined as the serum PSA level lower than the lowest serum PSA level during follow-up plus 2.0 ng/mL according to ASTRO Phoenix consensus definition. Experimental arm: Biochemical progression in the experimental/intervention arm is defined as a rising PSA level surpassing 0.2 ng/mL.

START OF ANTI-ANDROGEN TREATMENT

Anti-androgen treatment should be initiated among men with a PSA-doubling time of <12months when the PSA level surpasses 10 ng/mL, or upon symptoms or other clinical signs of disease progression. AA treatment includes continuous treatment with Bicalutamide 150 mg daily per os after initial prophylactic breast irradiation.

CASTRATION-RESISTANT PROSTATE CANCER (CRPC)

Definition of castration-resistant prostate cancer is based on EAU guidelines as follows: Castrate levels of serum testosterone (<1.7nM). Three consecutive PSA rises at least 1 week apart, resulting in two 50% increases over the nadir, with a PSA > 2 ng/mL.

SECOND-LINE THERAPY

Second line therapy at the time of progression will be started at the discretion of the treating clinician and will follow the local practice. Decisions should, however, be made at multidisciplinary therapy conferences. Effort should be put into classifying the progression as local or distant before starting second line therapy since one primary endpoint will be metastasis free survival.

DISTANT METASTASES

After each follow-up visit, the patient is categorized as having

- a) No suspected distant metastasis
- b) Suspected distant metastasis
- c) Confirmed distant metastasis

QUALITY OF LIFE

Quality of life will be measured on four different axes (see separate Quality of Life questionnaire):

- a) Urinary health
- b) Sexual health
- c) Bowel health
- d) General psychological health

CAUSE OF DEATH

The following classification of deaths shall be attempted:

- a) Death from prostate cancer
- b) Death from other causes but with recurrent or metastatic prostate cancer
- c) Dead from other causes with no evidence of recurrent prostate cancer

SAFETY REPORTING

An adverse event is any untoward medical occurrence in a patient or to whom a medical product or surgical procedure has been administered, including occurrences that are not necessarily caused by or related to that product.

An adverse reaction is any untoward or unintended response to an investigational medical product related to any dose administered.

A serious adverse event (SAE) is an adverse event or adverse reaction that fulfills any of the following criteria:

- Results in death
- Is life-threatening
- Requires hospitalization or prolonging of existing hospitalization
- Results in persistent or significant disability or incapacity

Apart from assessing chronic side effects in the quality-of-life questionnaire, we will report serious adverse events during the treatment phase of the study (0 to 12 months) by **recording any adverse event possibly associated with per-protocol treatment requiring hospitalization on a specific SAE CRF form.** To validate this information, we will also use patient register information from inpatient care to assess frequency, duration, and causes of hospitalizations.

ASSESSMENT OF INTENSITY

Each AE is to be classified by the investigator as mild, moderate or severe.
Mild: Acceptable. The subject is awareness of symptoms or signs, but they are easy tolerated.
Moderate: Disturbing. The AE is discomfort enough to interfere with usual daily activity.

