This is a prospective, multi-center, open randomized phase III trial complying with international guidelines for the treatment of locally advanced prostate adenocarcinoma. Subjects will be randomized to either conventional treatment (radiotherapy+ ADT) or intervention treatment (i.e. surgical prostatectomy+ radiotherapy if necessary). Each subject will follow the guidelines regarding the timing of treatment, additional postoperative radiotherapy, the dosing of radiotherapy, and adjuvant treatment such as androgen deprivation therapy. All surgical patients will be managed according to standard operating procedures at each local operating theatre. The total study duration will be 13 years. Each subject will be followed up for 10 years. The enrolment period extend to three years. The amount of visits sums to 14 times. The planned start of screening is March 2014, planned end of enrolment March 2017. The planned end of follow up, start of data analysis and report writing: 2027-2028.

STUDY OBJECTIVES

PRIMARY OBJECTIVE

The main purpose of this study is to evaluate whether cause-specific survival is better after primary radical prostatectomy, with the addition of adjuvant or salvage radiotherapy and endocrine treatment if indicated, than after primary radiation and endocrine treatment.

SECONDARY OBJECTIVES

To compare metastasis-free survival, overall survival, quality of life and health-services requirements (measured has hospitalization rates and analgesic consumption) between the two intervention arms.

ENDPOINTS

PRIMARY ENDPOINT

Cause-specific survival (CSS). Mortality and mortality causes will be ascertained from the nationwide Cause-of-Death Register.

SECONDARY ENDPOINTS

- Metastasis free survival
- Overall survival
- Quality-of-life, assessed through repeated questionnaires
- Time to Castration-Resistant Prostate Cancer (ascertained at follow-up visits)
- Time to biochemical progression (ascertained at follow-up visits)
- Adverse events
- Annual DDD of analgesics, prescription databases
- Annual number of days of hospitalization (patient registers)
- Cardiovascular disease (patient register)

PLAN OF STUDY VISITS

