The plan of study visits is schematically depicted on page 24. Case Report Forms (CRFs) are web-based (eCRFs) as are the quality-of-life questionnaires, but paper questionnaires should be available for patients that prefer or have limited access to the internet. Apart from the randomized allocation of treatment, the documentation in eCRFs, and the quality-of-life questionnaires, the study does not entail examinations or visits outside standard clinical routine.

SCREENING, VISIT 1

The first assessment of eligibility is done either by a urologist or an oncologist. After assessment of eligibility for surgery/radiotherapy, the urologist refers to an oncologist, or vice versa, for second opinion and assessment of eligibility for the alternative treatment. It is preferable and beneficial for the inclusion rate if screening visit one and two are combined into one single coordinated visit. All subjects are logged in a 'screening visits log' in order to calculate screening failures and the reasons for failure.

SCREENING, VISIT 2

Before the second screening visit, a study nurse may give further study information to the patient. If the patient is considered eligible for either treatment and is willing to participate, the informed consent is signed.

INCLUSION AND RANDOMIZATION

Inclusion and randomization is done as soon as possible after the informed consent is signed, preferably within 24 hours.

- 1. The patient completes the **baseline quality-of-life questionnaire (QoL 0**).
- 2. The **inclusion form** is filled in to confirm that the inclusion criteria are met
- 3. The patient is **randomized to treatment A or B**. The randomization will be executed in strict sequence as their eligibility is confirmed. **The date of randomization marks day 0 of follow up.**
- 4. Clinical characteristics are documented in **eCRF #1**.
- 5. Anytime before surgery or neoadjuvant hormone treatment is started, blood and urine samples (50 ml each) shall be collected (see separate instructions).

TREATMENT PHASE

If the patient is randomized to radiotherapy, endocrine therapy is initiated as soon as possible. Otherwise, surgery is scheduled with high priority.

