- Surgery (intervention) arm (A): Perioperative data are registered in eCRF #2 at discharge from postoperative care. The remaining postoperative data will be added in eCRF #3 after the first follow-up visit at 6 to 12 weeks postoperatively. Whenever the patient is subjected to postoperative radiotherapy, eCRF Postop RT is completed.
- Radiotherapy (**reference**) arm (B): Patients in the radiotherapy group will have frequent visits for their fractioned treatment during a three-month period. Therapy data will be summarized in **eCRF #4** by the end of the treatment period around 6 months after randomization.

Serious adverse events during treatment phase (0 to 12 months after randomization) leading to hospitalization are documented in a specific CRF for SAEs (**eCRF SAE**)

[figure not shown]
FOLLOW-UP PHASE

The first follow-up visit/contact common for both treatment arms is at 12 months after randomization. The visit/contact follows standard clinical routine. PSA is measured. **eCRF #5** is completed. Patients respond to the one-year QoL questionnaire (QoL 1).

Patients are followed up every 6 months during the second year after randomization, and annually thereafter. **eCRF #5** is then completed annually. Evaluation always includes PSA testing to assess biochemical progression. Before completing **eCRFs #5 at 5 and 10 years after randomization**, a bone scan (or other routinely used imaging method for detection of bone metastases) is performed for those with a PSA that has risen above PSA nadir + 2.0 ng/mL.

An off-study form is completed whenever a patient leaves follow up. For patients dying during follow up, an off-study form is only necessary if the cause of death cannot validly be ascertained through register-based follow up.

SPCG-15 STUDY FLOW CHART

ENROLMENT OF PATIENTS

Participating centers shall aim to include all patients who fulfill the requirements for randomization. No randomization shall be made until all inclusion criteria are met. The total number of patients to be randomized is 1,200.

INCLUSION CRITERIA

Subject will be included in the study if he meets ALL of the following inclusion criteria:

- 1. Age \leq 75, at the time of randomization
- 2. Newly diagnosed prostatic adenocarcinoma morphologically confirmed and untreated
- 3. The transrectal ultrasound (TRUS-guided) systematic biopsy with at least 10 cores or alternatively fewer but MR/TRUS fusion guided biopsies.

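### Time to biochemical progression has a different PSA event rule in each arm, so any between-arm comparison on those rules is biased against surgery

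*Protocol*

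**What the plan says.** The protocol's list of secondary endpoints includes "Time to biochemical progression (ascertained at follow-up visits"). Under Inclusion and Randomization, the clock is common to both arms: "The date of randomization marks day 0 of follow up".

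The event itself is set in the Biochemical Progression part of Definition of Clinical Events and Suggested Treatment, and it depends on the arm:

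- **Radiotherapy arm:** the Phoenix definition. Freedom from progression is worded as "No biological evidence of disease is defined as the serum PSA level lower than the lowest serum PSA level during follow-up plus 2.0 ng/mL", so the event is reaching nadir + 2.0 ng/mL.
- **Surgery arm:** "Biochemical progression in the experimental/intervention arm is defined as a rising PSA level surpassing 0.2 ng/mL".

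PSA is measured on the same schedule in both arms: at 12 months, and then "Patients are followed up every 6 months during the second year after randomization, and annually thereafter". The Follow-up Phase section also contains a PSA rule with no arm restriction. Before the 5-year and 10-year forms, bone imaging "is performed for those with a PSA that has risen above PSA nadir + 2.0 ng/mL".

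The protocol gives no common event definition for this endpoint, no sensitivity analysis with a single threshold, and no statement that the endpoint is descriptive only.

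**The concern.** A time-to-event comparison between randomized arms is interpretable only if the same course of disease counts as an event at the same time in either arm. Here it does not. A man whose PSA rises steadily through 0.2 ng/mL is an event at that point in the surgery arm. In the radiotherapy arm he is not an event until PSA is about ten times higher. Some men will cross the first level within follow-up and never reach the second.

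Any difference in time to biochemical progression would therefore mix the effect of treatment with the effect of the ruler. The second component has a known sign: it makes surgery look worse. At stake is a misleading secondary result in a trial that asks whether surgery is better.

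**Working it through.** The protocol states no figure for biochemical progression (no expected rate, hazard ratio or doubling time), so there is nothing of its own to reproduce.

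**Inputs from the protocol**
- Surgery threshold: 0.2 ng/mL, absolute.
- Radiotherapy threshold: nadir + 2.0 ng/mL.
- Time origin: randomization, both arms.
- Doubling time: the only value named is a treatment cut-off ("Anti-androgen treatment should be initiated among men with a PSA-doubling time of <12months when the PSA level surpasses 10 ng/mL"). It is not an expected value, so the doubling times below are assumptions.

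**Step 1. Lag on one curve.** If PSA rises exponentially with doubling time D, the time between the two thresholds is

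lag = D × log2((nadir + 2.0) / 0.2)

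- Nadir 0: ratio 2.0/0.2 = 10, or 3.32 doublings.
- Nadir 0.1: ratio 2.1/0.2 = 10.5, or 3.39 doublings.
- Nadir 0.2: ratio 2.2/0.2 = 11, or 3.46 doublings.

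Ten-fold is therefore the minimum, reached at nadir 0.

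**Step 2. Lag in months at nadir 0**

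| Assumed doubling time | Lag |
|---|---|
| 3 months | 3 × 3.32 = 10.0 months |
| 6 months | 6 × 3.32 = 19.9 months |
| 9 months | 9 × 3.32 = 29.9 months |
| 12 months | 12 × 3.32 = 39.9 months |
| 18 months | 18 × 3.32 = 59.8 months |

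The lag exceeds one year when D is above 12/3.32 = 3.6 months, and two years when D is above 24/3.32 = 7.2 months. With yearly visits, a very fast rise may pass both thresholds between two visits and be recorded at the same one. The surgery event is never recorded later.

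**Step 3. Illustration of the effect on a hazard ratio.** The same PSA curves were simulated in both arms and each arm was scored by its own rule over 10 years. All inputs are assumed: 40% or 60% of men relapse, exponential onset with mean 3 years, PSA 0.05 ng/mL at onset (so the radiotherapy threshold is 2.05), and a log-normal doubling time (log-scale SD 0.6). The true hazard ratio is 1.

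| Median doubling time | 40% relapse | 60% relapse |
|---|---|---|
| 6 months | 1.21 | 1.30 |
| 9 months | 1.40 | 1.54 |
| 12 months | 1.66 | 1.85 |

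The entries are spurious hazard ratios, surgery versus radiotherapy. With a 9-month median and 40% relapse, 25.4% in the surgery arm and 11.5% in the radiotherapy arm would be recorded as progressed by 5 years, although the curves are the same.

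**Step 4. With one rule.** If both arms use the same threshold, identical curves give identical event times: lag 0 and hazard ratio 1.

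**The case against.** **No comparison is actually stated.** The secondary objectives sentence names the outcomes to be compared, and biochemical progression is not among them. No test is specified for it, and a statistical analysis plan that is not at hand might add a common-threshold analysis. This stands, and it is why the point is conditional. It does not remove the point: this is a listed endpoint of a two-arm trial, and the protocol itself fixes the event by arm.

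**Each rule suits its treatment.** The prostate stays in place after radiotherapy and is removed by surgery. That can explain separate rules for clinical follow-up. It does not make the two times comparable.

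**The lag is hypothetical.** It assumes one uninterrupted exponential curve. In practice, surgical patients may receive postoperative radiotherapy with 18 months of bicalutamide, and reference-arm patients receive 3 + 3 months of maximal blockade followed by 18 months of further endocrine treatment, with prolongation allowed. PSA is thus hormonally lowered in both arms, though not equally. This stands: the figures show what the definitions alone do, not the expected net difference.

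**Stronger readings that a reader might infer, but which the documents do not support:**
- *That 0.2 ng/mL marks entry to deferred radiotherapy.* The algorithms are in Figures 1 and 2, which are not visible in the text at hand, and the visible text gives no such trigger.
- *That the unequal definition leads to earlier work-up and treatment after surgery.* The imaging trigger, the anti-androgen rule and the CRPC definition carry no arm restriction. Only the conference depends on biochemical progression ("all patients with suspected biochemical progression or CRPC shall be discussed in multidisciplinary therapy conferences"), and it covers suspected progression.
- *That the comparison would say nothing about efficacy.* The sign of the bias is known, so a null result or one favoring surgery would still be informative.

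**Conclusion.** The definitions are not comparable between arms, and the direction of the resulting bias is certain: on the same rising PSA curve the surgery threshold is crossed first, by at least 3.3 doublings. The length in time rests on assumed doubling times: about 10 months at 3 months, 20 at 6 months and 40 at 12 months. The spurious hazard ratios of about 1.2 to 1.9 rest on further assumptions and are illustrative only.

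The finding is limited to time to biochemical progression, one of nine secondary endpoints, and applies if the arms are compared on it. Cause-specific survival does not use this definition. The point should be fixed before any such comparison, but it does not undermine the trial's main question.

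**What to change.** State in the protocol that any between-arm comparison of time to biochemical progression uses one event rule in both arms. An example is the first PSA above nadir + 2.0 ng/mL, timed from randomization, with nadir taken as the lowest PSA recorded during follow-up up to that visit. This threshold already serves both arms as the imaging trigger. Report the 0.2 ng/mL and Phoenix definitions as arm-specific descriptive measures, without a between-arm test. Fix the rule before the arms are compared. Clinical follow-up and treatment triggers stay as they are.

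**Cost.** The change needs a wording amendment and a derivation from PSA values already collected, with no new visits or tests. The downside is fewer and later events in the surgery arm than under 0.2 ng/mL. Part of the reason is that postoperative radiotherapy with bicalutamide may be given before nadir + 2.0 ng/mL is reached, and this may delay or prevent the event. The endpoint then compares whole treatment strategies rather than the first local treatment alone, and the report should say so.
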